## 8.3 ADVERSE EVENTS AND SERIOUS ADVERSE EVENTS

### 8.3.1 DEFINITION OF ADVERSE EVENTS (AE)

An adverse event (AE) is defined as any untoward medical occurrence associated with the use of an intervention in humans, whether or not considered intervention-related (21 CFR 312.32 (a)). Short-term AEs associated with the study include "cybersickness," a transient form of motion sickness that affects up to one in four people upon entering a VR environment. Cybersickness most commonly presents with a short-term feeling of dizziness that typically subsides quickly. There are no anticipated long-term AEs from participating in this study. A comprehensive list of all potential cybersickness symptoms can be found below:

- Nausea
- Fatigue
- Eyestrain
- Blurred vision
- Difficulty focusing
- Dizziness
- Vertigo (a sensation of spinning dizziness, as though the room or surrounding environment is spinning)
- Headache
- Fullness of the head
- Difficulty concentrating
- Postural instability

In addition, in rare situations, one may have an allergy to the facial interface that generates a rash, which typically resolves without any medication in under 24 hours. There is also the possibility of a participant experiencing neck pain as a result of using the headset for an extended period of time. Participants will be informed of ways to mitigate the possibility of neck pain while using the headset.

### 8.3.2 DEFINITION OF SERIOUS ADVERSE EVENTS (SAE)

A serious adverse event (SAE) or suspected adverse reaction is considered "serious" if, in the view of either the investigator or sponsor, it results in any of the following outcomes: death, a life-threatening adverse event, inpatient hospitalization or prolongation of existing hospitalization, a persistent or significant incapacity or substantial disruption of the ability to conduct normal life functions. Important medical events that may not result in death, be life-threatening, or require hospitalization may be considered serious when, based upon appropriate medical judgment, they may jeopardize the

participant and may require medical or surgical intervention to prevent one of the outcomes listed in this definition. We do not expect any serious adverse events with a virtual reality intervention.

### 8.3.3 CLASSIFICATION OF AN ADVERSE EVENT

#### 8.3.3.1 SEVERITY OF EVENT

For adverse events (AEs) the following guidelines will be used to describe severity.

- **Mild** – Events require minimal or no treatment and do not interfere with the participant's daily activities.
- **Moderate** – Events result in a low level of inconvenience or concern with the therapeutic measures. Moderate events may cause some interference with functioning.
- **Severe** – Events interrupt a participant's usual daily activity and may require systemic drug therapy or other treatment. Severe events are usually potentially life-threatening or incapacitating. Of note, the term "severe" does not necessarily equate to "serious".

Research staff will call the patient if an event is noted in an event assessment that is sent on a weekly basis. Nothing more than mild side effects that do not require medical treatment are expected.

#### 8.3.3.2 RELATIONSHIP TO STUDY INTERVENTION

All adverse events (AEs) must have their relationship to study intervention assessed by the clinician who examines and evaluates the participant based on temporal relationship and his/her clinical judgment. The degree of certainty about causality will be graded using the categories below. In a clinical trial, the study product must always be suspect.

- **Related** – The AE is known to occur with the study intervention, there is a reasonable possibility that the study intervention caused the AE, or there is a temporal relationship between the study intervention and event. Reasonable possibility means that there is evidence to suggest a causal relationship between the study intervention and the AE.
- **Not Related** – There is not a reasonable possibility that the administration of the study intervention caused the event, there is no temporal relationship between the study intervention and event onset, or an alternate etiology has been established.

#### 8.3.3.3 EXPECTEDNESS

Research staff will be responsible for determining whether an adverse event (AE) is expected or unexpected. An AE will be considered unexpected if the nature, severity, or frequency of the event is not consistent with the risk information previously described for the study intervention. A detailed description of expectedness is provided in DSMP section 1.2.3.

### 8.3.4 TIME PERIOD AND FREQUENCY FOR EVENT ASSESSMENT AND FOLLOW-UP

The occurrence of an adverse event (AE) or serious adverse event (SAE) may come to the attention of study personnel during review of weekly event assessments by a study team member as well as on Day 1. We will employ a general question to allow the patient to provide an event description without bias by presupposing the nature of the event, as follows:

- 1) During the past 14 days, have you experienced anything uncomfortable, distressing or upsetting as a result of using the VR headset?
  - a. Yes
  - b. No
- 2) If Yes please describe what happened. A research staff member will follow-up with you as soon as possible to learn more.
  - a. [open text]

A designated CRC will review the REDCap dashboard for completed AE assessments on a daily basis throughout the work week. Once they find a completed event assessment form, they will follow-up with a phone call. The following information be obtained from the patient during the call: onset of potential adverse event, event description, when they last used the VR headset, how long they used the headset, when they stopped using the headset, severity of the potential AE, outcome of the potential AE (see categories, below), time until resolution/stabilization of event, the perceived relationship of the event to the study intervention, whether or not the event was expected (Y/N), whether it was serious.

The outcome can be labeled using one of the following categories:

- Recovered, without treatment
- Recovered, with treatment
- Still Present, no treatment
- Still Present, being treated
- Residual effect(s) present-no treatment
- Residual effect(s) present-being treated

Research staff will record all reportable events with start dates occurring any time after informed consent is obtained until 7 (for non-serious AEs) or 30 days (for SAEs) after the last day of study participation. Please see section 1.3 in DSMP for instructions on how events will be followed for outcome information until resolution or stabilization.

---

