#### DSMB

All AEs, regardless of their severity, relatedness or expectedness, are reported in aggregate as part of the routine Data and Safety Monitoring Report to the NIAMS and DSMB, twice per year.

A detailed description of procedure for collecting event is in section 1.2.3 of the DSMP.

---

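### The adverse event question printed in the protocol elicits only events the participant blames on the headset, and its 14-day recall matches neither the weekly wording nor the Schedule of Activities

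*Protocol*

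**What the plan says.** **What counts as an AE.** Protocol 8.3.1 defines it as "any untoward medical occurrence associated with the use of an intervention in humans, whether or not considered intervention-related". Section 8.3.3.2 has a clinician assign relatedness and provides a not-related category. Under 8.3.5, "All AEs, regardless of their severity, relatedness or expectedness, are reported in aggregate" to NIAMS and the DSMB twice a year.

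**How AEs are asked about.** Section 8.3.4 prints one question: "During the past 14 days, have you experienced anything uncomfortable, distressing or upsetting as a result of using the VR headset". A yes leads to an open-text description and a staff phone call. That call collects, among other items, the perceived relationship to the intervention. The section presents this as a general question meant not to steer the participant.

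**How often, and over what period.** Section 8.3.3.1 refers to "an event assessment that is sent on a weekly basis". Section 8.3.4 says events may come to light "during review of weekly event assessments by a study team member as well as on Day 1". The question itself opens with "During the past 14 days". The Schedule of Activities (1.3) places event assessments at Days 1, 7, 15, 21, 30, 45, 60, 75 and 90, each with a +6-day window.

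**Recording period.** Section 8.3.4 runs it from informed consent to 7 days (non-serious AEs) or 30 days (SAEs) after the last day of participation.

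**Analysis.** Safety is summarised by arm for all randomized patients (protocol 9.3, SAP 4.2), descriptively and without testing (protocol 9.4.4, SAP 4.7). The SAP adds no other means of eliciting events.

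**The concern.** The definition, the relatedness step and the DSMB commitment all assume that events arrive first and are judged for cause afterwards. The scripted question reverses that order. A participant who falls or is admitted to hospital, and sees no link to the headset, answers no truthfully. Nothing then reaches the clinician, so the not-related category can be filled only by events the participant had already blamed on the headset. A related event that the participant does not recognise as such is lost in the same way.

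Protocol 2.2 describes the longer-term safety of therapeutic VR as largely untested and makes its assessment a purpose of this trial. AE and SAE tables built on this item would fall short of the scope the protocol promises the DSMB.

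The second, smaller matter is that weekly sending, a 14-day recall and 15-day spacing cannot all describe one procedure. Site staff and readers cannot tell which days of follow-up were asked about.

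**Working it through.** **Attribution (no arithmetic; the sections compared)**

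| Step | Protocol section | Restricted to headset-caused events? |
|---|---|---|
| Definition of an AE | 8.3.1 | No |
| Scripted question | 8.3.4 | Yes, in the participant's judgement |
| Relatedness | 8.3.3.2 | No; the clinician decides |
| Report to DSMB | 8.3.5 | No |

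The only restricted step is the one that feeds the rest. Two groups show the effect. Section 7.2 keeps people who stop VR but go on answering surveys; they would properly answer no about a later fall. Section 8.3.4 records events from consent, but the kit arrives only at enrolment, so a headset-conditioned item cannot elicit screening-week events. At the other end, no event assessment is scheduled after Day 90, although recording continues for 7 or 30 days.

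**Recall coverage.** The plan gives no figure to reproduce. For consecutive completed assessments:

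uncovered days = max(0, interval − 14)

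*Weekly text (8.3.3.1, 8.3.4).* Interval 7: max(0, 7 − 14) = 0. Alternate surveys 6 days late give a longest interval of 7 + 6 = 13, still 0. One missed survey gives 14 − 14 = 0. The windows overlap, so each day is asked about roughly twice and one event can be reported twice.

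*Schedule of Activities, answered on the due day.* The intervals are 6, 8, 6, 9, 15, 15, 15 and 15 days. The first four leave 0. The last four leave 15 − 14 = 1 each (Days 31, 46, 61 and 76), 4 in total.

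*Schedule of Activities, within the +6-day windows.*
- Longest interval after Day 30: 15 + 6 = 21, leaving 7. The interval from Day 21 to Day 30 can reach 9 + 6 = 15, leaving 1.
- Most unfavourable total: for example Day 60 answered on Day 66 and Day 90 on Day 96, the rest on time. The intervals from Day 30 are 15, 21, 9 and 21, so 1 + 7 + 0 + 7 = 15 uncovered days.
- Most favourable total: answers on Days 21, 34, 48, 62, 76 and 90 are all in window. The intervals are 13, 14, 14, 14 and 14, so 0 uncovered days.

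*Schedule of Activities, one survey missed, the rest on the due day.*
- Day 45, 60 or 75 missed: one interval of 30 leaves 16 where two intervals had left 1 + 1 = 2. That adds 14, for a total of 18.
- Day 30 missed: the interval from Day 21 to Day 45 is 24 and leaves 10 where 0 + 1 = 1 had been left. That adds 9, for a total of 13.

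**The case against.** **Other routes exist.** Section 8.3.5 refers to DSMP section 1.2.3 for the detailed collection procedure, and that document was not available. Section 8.3.4 does not call the form the exclusive route. Section 8.2 promises follow-up for any AE, and a PROMIS Depression score above 70 triggers a physician contact whatever its cause. A reader might infer that unrelated events are never captured; the documents do not support that. Nor do they support saying that worsening pain or mood goes unseen, because PROMIS Pain Interference and Depression are collected repeatedly. What remains is narrower. Section 8.2 names no mechanism for its general promise, the depression and TAPS alerts cover only their own domains, and the content of the Discontinuation of Treatment Questionnaire is not shown. None of these is described as a general enquiry about health events.

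**The recall gap depends on the schedule.** A reader might infer that a 14-day recall loses follow-up days in itself, or that 4 days is the minimum lost. Neither holds: the weekly text leaves none, and in-window answering on the schedule days can also leave none. An event on a single uncovered day may well be mentioned anyway.

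**Bias between arms.** A reader might infer that attribution differs between the immersive and 2-D arms and distorts the safety comparison. This is possible, but no figure in the documents supports it, and participants are blinded.

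**Consequence and timing.** Protocol 10.1.7 treats the intervention as not greater than minimal risk, safety is descriptive, and no efficacy inference is touched. Protocol 8.1 planned randomization from 10/1/2020 to 9/5/2023 and this version is dated 19 October 2023, so on those dates most participants had already answered the item. Changing it now mixes two ways of collecting events. These points stand. They affect urgency and the form of the remedy, not the conflict in wording.

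**Conclusion.** The conflict over attribution is firm and rests on the protocol's text alone: the one AE question it prints is narrower than its AE definition, its relatedness procedure and its DSMB commitment. AEs and SAEs that participants do not link to the headset are not systematically elicited by anything described in the protocol or SAP. How many events this affects cannot be estimated from the documents, and DSMP section 1.2.3 could change the conclusion if it sets out a general enquiry.

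The frequency and recall point is a three-way inconsistency of modest and conditional size. There are 0 uncovered days under weekly sending. On the Schedule of Activities days there are 4 if every survey is answered when due, and 0 to 15 over follow-up depending on timing within the windows; missing Day 45, 60 or 75 adds 14 to the on-time figure. These counts assume that participants apply the 14 days literally.

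**What to change.** 1. Reword the item to ask about any new or worsened health problem, injury, or hospital or emergency visit since the last completed assessment, with no attribution clause. Recall tied to the last completed assessment removes both gaps and overlaps, whatever the frequency.
2. Collect the perceived link to the headset only as a follow-up item, and leave relatedness to the clinician as in 8.3.3.2.
3. Reconcile 8.3.3.1, 8.3.4 and the Schedule of Activities to one frequency, check DSMP section 1.2.3 against the result, and say how events after Day 90 are to be learned of within the recording period.
4. For participants already assessed with the existing item, state in safety reports that solicited AEs were limited to participant-attributed events. If the item changes during follow-up, show the two ascertainment periods separately. If follow-up is complete, this disclosure is the main remedy; the sponsor could also consider checking available EHR data for hospitalizations.

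The cost is one REDCap item, text edits and a reporting note. The downside is more unrelated reports, each needing a staff call; the documents give no basis for estimating how many.

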### 8.3.5 ADVERSE EVENT REPORTING

#### Cedars-Sinai IRB

If a mild or moderate event occurs it does not need to be submitted to the Reportable New Information (RNI). If the event is an unexpected (not usually associated VR side effects) or severe event (requiring treatment), an AE will be submitted to the IRB as soon as possible but within at least 10 working days.

#### DSMB

All AEs, regardless of their severity, relatedness or expectedness, are reported in aggregate as part of the routine Data and Safety Monitoring Report to the NIAMS and DSMB, twice per year.

A detailed description of procedure for collecting event is in section 1.2.3 of the DSMP.

---

### 8.3.6 SERIOUS ADVERSE EVENT REPORTING

SAEs will be submitted to the Cedars-Sinai IRB via RNI as soon as possible by study coordinators, but no later than 10 business days from the Principal Investigator's or study team's awareness of the event,

incident, information or outcome. In addition, SAEs will be reported to the DSMB and NIAMS via the NIAMS executive secretary within 48 hours of becoming aware of the event.

#### 8.3.7 REPORTING EVENTS TO PARTICIPANTS

N/A

#### 8.3.8 EVENTS OF SPECIAL INTEREST

N/A

#### 8.3.9 REPORTING OF PREGNANCY

N/A

### 8.4 UNANTICIPATED PROBLEMS

#### 8.4.1 DEFINITION OF UNANTICIPATED PROBLEMS (UP)

The Office for Human Research Protections (OHRP) considers unanticipated problems involving risks to participants or others to include, in general, any incident, experience, or outcome that meets all of the following criteria:

- Unexpected in terms of nature, severity, or frequency given (a) the research procedures that are described in the protocol-related documents, such as the Institutional Review Board (IRB)-approved research protocol and informed consent document; and (b) the characteristics of the participant population being studied;
- Related or possibly related to participation in the research (“possibly related” means there is a reasonable possibility that the incident, experience, or outcome may have been caused by the procedures involved in the research); and
- Suggests that the research places participants or others at a greater risk of harm (including physical, psychological, economic, or social harm) than was previously known or recognized.

This definition could include an unanticipated adverse device effect, any serious adverse effect on health or safety or any life-threatening problem or death caused by, or associated with, a device, if that effect, problem, or death was not previously identified in nature, severity, or degree of incidence in the investigational plan or application (including a supplementary plan or application), or any other unanticipated serious problem associated with a device that relates to the rights, safety, or welfare of subjects (21 CFR 812.3(s)).

#### 8.4.2 UNANTICIPATED PROBLEM REPORTING

Study coordinators will report unanticipated problems (UPs) to the Cedars-Sinai IRB as a RNI submission as soon as possible by study coordinators, but no later than 10 business days from the Principal Investigator's or study team's awareness of the event, incident, information or outcome. UPs include SAEs and AEs, which are both unexpected and possibly related to the research as well as SAEs and AEs that meet the definition of a Research-Related Subject Injury (RRSI) – a medical condition that is caused by and/or directly related to the research study (i.e., the condition would not have existed “but for” the subject's participation in the study), and requires diagnosis or treatment.

The UP report will include the following information:

- Protocol identifying information: protocol title and number, PI's name, and the IRB project number;
- A detailed description of the event, incident, experience, or outcome;
- An explanation of the basis for determining that the event, incident, experience, or outcome represents an UP;
- A description of any changes to the protocol or other corrective actions that have been taken or are proposed in response to the UP.

UPs will also be reported to NIAMS and the DSMB via the NIAMS executive secretary within 48 hours of the PI becoming aware of the event.

---

#### 8.4.3 REPORTING UNANTICIPATED PROBLEMS TO PARTICIPANTS

N/A

### 9 STATISTICAL CONSIDERATIONS

#### 9.1 STATISTICAL HYPOTHESES

- **Primary Efficacy Endpoint(s):**

Primary Outcome: Pain interference over time as measured by PROMIS-Pain Interference 8a (T-Scored, Continuous).

Hypothesis: Immersive VR (Skills-based VR or Distraction VR) will lead to a greater improvement in pain interference than Sham VR over 30-day period.

Comparisons: Superiority for both of the following (1) Distraction VR therapy vs. sham VR therapy; (2) skills-based VR therapy vs. sham VR therapy.

Additional comparison: If there is a statistically significant difference in Skills based VR vs Sham VR, then a third test will be completed (3) Skills-based VR therapy vs Distraction VR therapy.

- **Secondary Efficacy Endpoint(s):**

Secondary Outcome: Pain interference over time as measured by PROMIS-Pain Interference 8a (T-Scored, Continuous).

Hypothesis: Immersive VR (Skills-based VR or Distraction VR) will lead to a greater improvement in pain interference than Sham VR at Day 60 and Day 90.

Comparisons: Superiority for both of the following (1) Distraction VR therapy vs. sham VR therapy; (2) skills-based VR therapy vs. sham VR therapy.

Additional comparison: If there is a statistically significant difference in Skills based VR vs Sham VR then a third test will be completed (3) Skills-based VR therapy vs Distraction VR therapy.

Secondary Outcome: Pain catastrophizing over time as measured by Pain Catastrophizing scale (PCS) short form.

Hypothesis: Skills-based VR will lead to a greater improvement in Pain catastrophizing than distraction-based VR or Sham VR.

Comparisons: Superiority for both of the following (1) Distraction VR therapy vs. sham VR therapy; (2) skills-based VR therapy vs. sham VR therapy, if there is a statistically significant difference in Skills based VR vs Sham VR then a third test will be completed (3) Skills-based VR therapy vs Distraction VR therapy

Secondary Outcome: Anxiety over time as measured by PROMIS Anxiety.

Hypothesis: Skills-based VR will lead to a greater improvement in PROMIS Anxiety than distraction based VR or Sham VR.

Comparisons: Superiority for both of the following (1) Distraction VR therapy vs. sham VR therapy; (2) skills-based VR therapy vs. sham VR therapy, if there is a statistically significant difference in Skills based VR vs Sham VR then a third test will be completed (3) Skills-based VR therapy vs Distraction VR therapy

Secondary Outcome: Quality of sleep over time as measured by PROMIS Sleep Disturbance.

Hypothesis: Skills-based VR will lead to a greater improvement in sleep quality than distraction based VR or Sham VR.

Comparisons: Superiority for both of the following (1) Distraction VR therapy vs. sham VR therapy; (2) skills-based VR therapy vs. sham VR therapy, if there is a statistically significant difference in Skills based VR vs Sham VR then a third test will be completed (3) Skills-based VR therapy vs Distraction VR therapy

Secondary Outcome: Comparing the change from study baseline to Day 90 in weekly MME of prescribed medication.

Question: Which intervention is more effective in reducing opioid prescriptions of Morphine Milligram Equivalents (MME) or greater?

Hypothesis: We believe that Skills-based VR will have a statistically significant decrease in opioid use in comparison to distraction-based VR and Sham VR.

Comparisons: Superiority for both of the following (1) Distraction VR therapy vs. sham VR therapy; (2) skills-based VR therapy vs. sham VR therapy, if there is a statistically significant difference in Skills based VR vs Sham VR then a third test will be completed (3) Skills-based VR therapy vs Distraction VR therapy

